| INVESTIGATOR/TRIAL LOCATION | US, Canada |
| PHASE OF DEVELOPMENT | Phase IV |
| STUDY OBJECTIVE(S) | 
Primary Objective
 
 • Demonstrate clinical benefit of Toujeo in achieving individualized HEDIS HbA1c targets (<8% if age ≥ 65 years or with defined comorbidities (as listed in Appendix G) or otherwise <7%) at 6 months without documented symptomatic (BG ≤ 70mg/dl) or severe hypoglycemia at any time of day from baseline to 6 months in uncontrolled insulin naïve patients with type 2 diabetes initiating basal insulin therapy in a real world setting. 
Secondary Objectives
 
Secondary objectives are to compare Toujeo to other commercially available basal insulins at 6 and 12 months after initiating insulin therapy in a real world setting in terms of:
 
 • Patient persistence with assigned basal insulin therapy, • Risk of hypoglycemia including the incidence and rate of documented symptomatic and severe hypoglycemia, • Changes in HbA1c, fasting plasma glucose, body weight, • Differences in patient and provider reported outcomes (including Diabetes Treatment Satisfaction Questionnaire Status and Change Versions [DTSQs and DTSQc]), Hypoglycemia Patient Questionnaire, and patient and provider reported Global Effectiveness Scale (GES), • Healthcare resource utilization including hospitalizations and emergency department or other provider visits and healthcare costs. |
| STUDY DESIGN | 
Potential study patients within designated practice sites who meet eligibility criteria may be identified by review of either payer or provider data bases. The inclusion/exclusion criteria will be applied to relevant databases to identify appropriate subjects with 12 months of baseline medical data available and who had actively sought care at the site in the last 12 months.
 
Achieve Control includes a planning phase and the prospective study phase. During the planning phase of the trial, payer, research organization, and HCP databases are reviewed to identify appropriate sites and patients eligible for the study. Patients may also be identified through ongoing review of these databases including at the site level on an ongoing basis during the trial. Patients will be screened at the practice site to determine eligibility for study enrollment. Patients will be assigned to one of two treatment groups using a
 |

| | |
|--|---|
| | 
patient-level randomization. Given the potential impact of certain variables on the primary endpoint, randomization will be stratified by individualized HbA1c target (<8%/<7%), SU use ever (y/n), GLP-1 RA use ever (y/n) and baseline HbA1c (<9%/≥9%).
 
The two treatment arms of the study will be:
 
 1) Toujeo with its available patient support program, 2) Commercially available insulin detemir (Levemir®) or insulin glargine-U100 (Lantus®) with or without a patient support program. 
Randomization will be 1:1 between the two arms of the study and the choice of comparator basal insulin will be based on the usual practice at the clinical site and not by randomization.
 
The study will include a 6 month treatment period ending in assessment of the primary and secondary endpoints followed by a 6 month extension period for assessment of certain additional endpoints. It will also include an interim analysis (IA) for overwhelming efficacy on the primary endpoint, planned to be conducted when approximately 1800 patients have been randomized and completed their 6-month visit. If the targeted sample size (1800) cannot be reached, it could be considered to include a lower number of patients, however not below 1700. In this case, the nominal significance level to be spent at interim and at final 6-month analyses would be recalculated accordingly before the database lock for IA.
 
An independent Data Monitoring Committee (DMC) will review data from this IA.
 
Dose regimen: Patients will be initiated on basal insulin therapy per the prescribing instructions for each insulin and titrated to a target fasting glucose consistent with the individualized HbA1c target according to the typical protocol used at each site and investigator discretion.
 
Financial support will be provided by Sanofi for the cost of commercially available basal insulin as well as for Toujeo.
 
Collection of hypoglycemia events and symptoms:
 
A glucometer with wireless data transmission capabilities will be used to collect self-measured plasma glucose (SMPG) including SMPG associated with hypoglycemic symptoms. An electronic diary (eDiary) will be used to record the symptoms of hypoglycemia and other relevant clinical information.
 |
| 
STUDY POPULATION
 
Main selection criteria
 | 
Inclusion criteria:
 
 ● Patients with T2DM, as defined by the ADA/WHO, diagnosed for at least 1 year at the time of the screening visit, insufficiently controlled after at least 1 year of treatment with 2 or more of the following: oral agents (metformin, sulfonylureas, thiazolidinediones, DPP-4 inhibitors, or SGLT-2 inhibitors) or GLP-1 receptor agonists for daily use and approved for use with insulin (Victoza®, Byetta®, Adlyxin®). ● Adult patients who have signed an Informed Consent Form and Health Insurance Portability and Accountability Act (HIPAA) Authorization Form 
Exclusion criteria
 
 ● HbA1c <8.0% or >11.0%, ● Males or females <18 years of age, ● Type 1 diabetes mellitus, |

| | |
|---|--|
| | 
 ● Any clinically significant abnormality identified on physical examination, laboratory tests, or vital signs at the time of screening, or any major systemic disease resulting in short life expectancy that in the opinion of the Investigator would restrict or limit the patient's successful participation for the duration of the study, ● Use of any product containing insulin (Lantus, Levemir, Humulin®, Novolin®, Humalog®, Novolog®, Apidra®, Afrezza®, Toujeo®, Tresiba®) since the time of diagnosis with T2DM prior to the time of screening other than temporary use such as during a pregnancy or hospitalization or short term outpatient use (≤10 days) during an acute medical event, ● Use of oral hypoglycemic agents other than those noted in the inclusion criteria; GLP-1 receptor agonists for weekly use (Trulicity®, Tanzeum®, Bydureon®), or not approved for use with insulin, or any investigational agent (drug, biologic, device) within 3 months prior to the time of screening, ● All contraindications to commercially available insulin therapy or warnings/precautions of use as displayed in the respective national product labeling for these products, ● Pregnancy or lactation, ● Women of childbearing potential with no effective contraceptive method. |
| Total expected number of patients | 3324 patients (1662 per arm), 160 from Canada Approximately 439 sites in US, 20 sites in Canada |
| STUDY TREATMENT(s) | |
| Investigational medicinal product(s) Formulation | Tested Drug: Toujeo/HOE901-U300 will be commercially available 300 U/mL insulin glargine solution for subcutaneous (sc) injection in 1.5 ml cartridges in the marketed Toujeo SoloSTAR® pen device. The disposable pen injector allows for dose setting in the range of 1-80 U with minimum dose increments of 1.0 U. Dilution or mixing of Toujeo with other insulin is not allowed. Control Drugs: Comparator basal insulins (Lantus/Levemir) will be commercially available formulations and used according to label. |
| Route(s) of administration | Tested drug or Control drugs: Insulin glargine given as either commercially available Toujeo/HOE901-U300 or Lantus U100 will be self-administered by sc injection once daily in the morning or evening according to label. Commercially available Levemir will be self- administered by sc injection once or twice daily in the morning or evening according to local label. |

| | |
|---|--|
| 
Dose regimen
 | 
Tested drug or Control drugs:
 
Dosing of insulin glargine given as Toujeo/HOE901-U300 or Lantus U100 and dosing of Levemir will be titrated to a target fasting glucose consistent with the individualized HbA1c target according to the typical protocol used at each site and investigator discretion.
 
Initiation of the basal insulin will be done according to the label and titration will be done according to local guidelines and investigator discretion.
 
The titration regimen is to be done according to real world practice and there is no recommended or forced titration in the protocol.
 |
| 
Noninvestigational medicinal product(s) (if applicable)
 
Formulation
 | 
Patients in both treatment groups will continue with other anti-diabetes drugs as background therapy at the discretion of the investigator and consistent with labeling guidelines for use with insulin.
 |
| 
Route(s) of administration
 | 
Oral anti-diabetic agents
 
GLP-1 receptor agonists for daily use which are approved for use with basal insulin and are injectable (Victoza, Byetta, Adlyxin).
 |
| 
Dose regimen
 | 
According to label and at investigator discretion
 |
| 
ENDPOINT(S)
 | 
Primary endpoint
 
Proportion of patients with individualized HbA1c target attainment per HEDIS criteria (<8% if age ≥ 65 years or with defined comorbidities listed in Appendix G or otherwise <7%) at 6 months without documented or severe symptomatic (BG ≤ 70 mg/dl) hypoglycemia at any time of day from baseline to 6 months.
 
The individual components of individualized HbA1c target attainment and absence of any documented symptomatic or severe hypoglycemia (BG ≤70 mg/dl) will also be evaluated as supportive analyses to evaluate consistency.
 
Secondary endpoint(s)
 
 ● Change in HbA1c from baseline (obtained at screening visit within one week of study initiation) to 6 months, ● Proportion of patients who remain on assigned basal insulin therapy (persistent with assigned therapy) at 6 and 12 months, ● Proportion of patients with individualized HbA1c target attainment per HEDIS criteria at 6 months without documented symptomatic (BG <54 mg/dl) or severe hypoglycemia at any time of day from baseline to 6 months, ● Proportion of patients with individualized HbA1c target attainment (per HEDIS criteria) at 12 months without documented symptomatic (BG ≤70 mg/dl) or severe hypoglycemia at any time of day from baseline to 12 months, ● Proportion of patients with individualized HbA1c target attainment per HEDIS criteria at 12 months without documented symptomatic (BG <54 mg/dl) or severe hypoglycemia at any time of day from baseline to 12 months. |

| | |
|----------------------------|--|
| | 
Patient Reported Outcomes Endpoints:
 
 • Proportion of patient and provider reported “Excellent” or “Good” responses to GES question at 6 months and 12 months, • Average scores on total treatment satisfaction, hyperglycemia perception, and hypoglycemia perception from DTSQs at 6 months and 12 months, • Average scores on change in total treatment satisfaction, hyperglycemia perception, and hypoglycemia perception from DTSQc at 12 months, • Proportion of patients who report moderate or severe hypoglycemia since last visit on the Hypoglycemia Patient Questionnaire (questions 4 and 5) at 6 months and 12 months. 
Healthcare Utilization Endpoints:
 
 • Mean number and proportion of patients with hospitalizations over a 6 month and 12 month period, • Mean number and proportion of patients with emergency room visits over a 6 month and 12 month period, • Mean number of provider office visits and proportion of patients with specialty visits over a 6 month and 12 month period, • Mean overall and diabetes-related costs at 6 months and 12 months. 
Other endpoint(s)
 
 • Change in HbA1c from baseline to 12 months, • Change in fasting plasma glucose from baseline to 6 months and 12 months, • Change in body weight from baseline to 6 months and 12 months, • Basal insulin dose at 6 and 12 months. 
Safety:
 
Hypoglycemia will be classified in categories (Section 9.2.3.1):
 
 • Incidence of documented symptomatic (BG ≤ 70 mg/dl) nocturnal (0000-0559) hypoglycemia from baseline to 6 and 12 months, and 24-hour hypoglycemia from baseline to 12 months, • Rate of documented symptomatic (BG ≤ 70 mg/dl) hypoglycemia (24 hour and nocturnal) from baseline to 6 and 12 months, • Incidence and rate of documented symptomatic (BG <54) hypoglycemia (24 hour and nocturnal) from baseline to 6 and 12 months, • Incidence and rate of severe hypoglycemia (24 hour, per ADA definition) from baseline to 6 and 12 months. 
Other safety and tolerability analyses will include adverse events and serious adverse events as well as product technical complaint events (PTC). This will include injection site reactions, hypersensitivity reactions and vital signs.
 |
| ASSESSMENT SCHEDULE | See flow chart, Section 1.2 |

[figure not shown]
| | |
|-----------------------------------|--|
| STATISTICAL CONSIDERATIONS | 
Sample Size Determination:
 
An original sample size of 1635 patients per treatment arm would provide at least 90% power to demonstrate superiority with an absolute difference of at least 5.5% in favor of Toujeo versus comparator basal insulins in the proportion of patients reaching individualized HbA1c target at month 6 without a documented symptomatic ($BG \leq 70$ mg/dl) or severe hypoglycemic event from baseline to month 6, assuming 30% of patients enrolled have a target HbA1c <8 per HEDIS criteria due to being older or due to the presence of medical comorbidities, and the remaining 70% having a target HbA1c $<7\%$.
 
Due to the addition of the interim analysis the sample size will be increased to a total of 3324 patients (1662 patients per treatment group). The calculation takes into account one interim analysis using a group sequential approach with an efficacy boundary based on a gamma (-3) alpha spending function.
 
The number of patients meeting each of these criteria will be monitored via demographic and ICD-9 data to avoid significant deviations from the assumptions above.
 
The total sample size calculation of 3324 is based on the assumption of a maximum of a 33% overall (weighted average) response rate with Lantus, and at least a 5.5% increase in response rate with Toujeo, and assumes an overall 2-sided test with alpha-level 0.05 with an interim analysis performed on 1800 patients followed 6 months.
 
Analysis Populations:
 
The primary analysis will be performed on the Intent-To-Treat (ITT) population, which will comprise all randomized patients, irrespective of the treatment actually being received at the time of analysis.
 
Safety will be assessed on an as-treated population, defined as all randomized patients who actually received at least 1 dose or part of a dose of IMP, analyzed according to the treatment actually received.
 
Primary Analysis:
 
The proportion of patients reaching individualized HbA1c target at 6 months without documented symptomatic ($BG \leq 70$ mg/dl) or severe hypoglycemia will be compared between treatment groups using a logistic model with log link, adjusting for individualized HbA1c target ($<8\%/<7\%$) and other stratification factors used at randomization: SU use ever (y/n), GLP-1 RA use ever (y/n), and baseline HbA1c (as continuous). As a sensitivity analysis, a multivariate analysis will be performed, adding the following baseline characteristics BMI, Patient Activation Measure (PAM) as an assessment of patient engagement, duration of diabetes and age.
 
One interim analysis is planned for the purpose of overwhelming efficacy on the primary composite endpoint when 1800 patients have been randomized and completed their 6-month visit (54.2% information fraction), using a two-sided nominal significance level of 0.010 based on a Gamma (-3) alpha-spending function.
 
The final 6-month analysis will be conducted when all randomized patients (3324) have performed their 6-month visit. The two-sided nominal significance level to be used at this final 6-month analysis is 0.046.
 
Patients with missing HbA1c data at 6 months will be regarded as not having reached HbA1c target.
 |
|-----------------------------------|--|

| | |
|--|---|
| | 
In order to examine the consistency of the primary analysis, the individual components of HbA1c target attainment and absence of any documented symptomatic (BG \leq 70 mg/dl) or severe hypoglycemia will also be evaluated. The proportion of patients without documented symptomatic (BG \leq 70 mg/dl) or severe hypoglycemia will be compared between treatment groups using logistic regression, adjusting for randomization strata and other baseline characteristics as clinically appropriate. The proportion of patients reaching individualized HbA1c target will be analyzed as for the composite primary endpoint.
 
Further, a predictive subgroup identification method will be employed to identify subgroups of potential responders.
 
Analysis of secondary endpoints
 
Persistence:
 
• The incidence of patients completing the 6 month and the 12 month periods will be described by treatment arm,• The proportion of patients who withdraw at Month 6 and Month 12 will be analyzed by treatment group using a logistic regression methodology as described above,• Cumulative incidence of treatment discontinuation will be plots/estimates by treatment arm using a Kaplan-Meier (KM) by treatment arm,• Extent of exposure as well as treatment compliance will also be described by treatment arm. 
In addition, for US patients, a medication possession ratio (MPR) will be assessed based on number of days that patients had possession of study drug based on prescription date and days of supply. A MPR of 80% would be indicative of patients being persistent on study medication.
 
For patients from US and Canada where there is not data available for calculation of the MPR, the extent of study treatment exposure and compliance will be assessed and summarized by observance of the actual treatment received within the safety population.
 
The duration of exposure during the study will be the total number of days of administration of IMP, accounting for temporary drug discontinuation.
 
The duration of exposure to the open-label IMP during the study is defined as: (Date of the last IMP administration – date of the first IMP administration)+1.
 
Efficacy Endpoints:
 
The change in HbA1c from baseline to 6 months will be analyzed using a mixed-effect model with repeated measures (MMRM) approach under the missing at random framework, using an adequate contrast at Month 6. The model will include fixed categorical effects of treatment arm, visit, treatment-by-visit interaction, randomization strata: individualized HbA1c target (<8%/<7%), SU use ever (y/n), GLP-1 RA use ever (y/n), and baseline HbA1c (as continuous), as well as baseline HbA1c-by-visit interaction.
 
The change in fasting plasma glucose and bodyweight from baseline to 6 and 12 months will be analyzed in a similar fashion to the change in HbA1c.
 |
|--|---|

| | |
|--|--|
| | 
The proportion of patients with individualized HbA1c target attainment without hypoglycemia will be analyzed as described for the primary endpoint.
 
PROs:
 
Self-reported patient satisfaction and hypoglycemia (DTSQ and Hypoglycemia Patient Questionnaire): Satisfaction scores at 6 and 12 months will be compared between treatment groups using a MMRM approach as described for the continuous efficacy variables. To adjust for the baseline differences between treatment groups, logistic regression will be conducted, adjusting for randomization strata; individualized HbA1c target (<8%/<7%), SU use ever(y/n), GLP-1 RA use ever(y/n) and baseline HbA1c(as continuous).
 
Global Effectiveness Scale (GES): At each study endpoint, the proportion of patients and providers who reported “Excellent” or “Good” at 6 and 12 months will be analyzed using logistic regression as described previously.
 
Health resource utilization for each treatment group will be analyzed by descriptive analysis. Multivariate analysis will be used to evaluate the difference in health resource utilization and cost between treatment groups with adjustment for specific covariates.
 
Safety Endpoints:
 
The incidence of hypoglycemia will be analyzed using logistic regression, adjusting for randomization strata and other baseline characteristics as clinically appropriate and if the model permits.
 
The rate per patient-year of hypoglycemic events will be analyzed using an over-dispersed Poisson regression model, adjusting for randomization strata and other baseline characteristics as clinically appropriate and if the model permits.
 |
| 
DURATION OF STUDY PERIOD (per patient)
 | 
The prospective phase of the trial will consist of:
 
 ● 1 week screening period at site, ● 26 week (6 month) treatment period, ● 26 week (6 month) extension period, ● The maximum study duration will be 53 weeks per patient. |

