6.3 INTERIM ANALYSIS

One formal IA is planned for the purpose of overwhelming efficacy of primary endpoint when 1800 patients have been randomized and completed their 6 month visit (Day 180). Statistical operating characteristics of this analysis, including the α -spending function to control the Type I error, are described in the statistical considerations (see [Section 11.5](#)).

Limited efficacy data is available regarding the initiation of insulin treatment in a “Real World” or pragmatic study. Achieve Control is a study designed to provide data on the efficacy and safety of Toujeo in a “Real World” setting. The unique primary composite endpoint has clinical relevance for managed care organizations and the study will provide safety and efficacy data for health care providers in their usual practice setting, rather than a traditional RCT.

The unanticipated challenges of recruiting patients in this unique trial design have resulted in delayed enrollment. Based on the need for real life Toujeo data for informing the decision makers on insulin use in managed care organizations, the objective of the study and IA is to generate real world evidence for the purpose of healthcare reimbursement and scientific communication only.

Results of this IA will be reviewed by the DMC ([Section 6.4.1](#)). The DMC procedures will be done with the utmost possible care for protecting clinical data integrity and for maintaining the blinding of Sponsor representatives and trial team so as not to impact final interpretation of the study results.

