6.4 STUDY COMMITTEES

6.4.1 Data Monitoring Committee

An independent DMC will be in charge of reviewing the unblinded efficacy results of the interim analysis. The DMC will give appropriate recommendations to the Sponsor on whether overwhelming efficacy is reached or not for the primary composite endpoint. The DMC may make recommendations regarding any measures that may be required for ensuring the integrity of the study results during the execution of its primary mission including assessing the risk benefit.

Overwhelming efficacy will be shown if the p-value of the superiority test for comparison of Toujeo and comparator basal insulins on the primary endpoint is below 0.010 with a higher proportion of patients reaching the primary endpoint in the Toujeo group.

The corresponding power to show overwhelming efficacy at interim analysis under the alternative hypothesis is of 45%.

If overwhelming efficacy is not shown (probability of 55% under the alternative hypothesis) the Sponsor would not see the unblinded data, and no results would be communicated. If

overwhelming efficacy is shown (probability of 45% under the alternative hypothesis) the Sponsor would see the data, and results would be communicated in agreement with the DMC. It could be considered to stop the recruitment (total sample size at that time estimated to be between 2600-3000 patients). However, study participation for patients already recruited would continue as planned. In either case (superiority achieved at interim or not), the study will continue up to month 6 and up to month 12 as planned, with analyses performed on whole study population.

The DMC consists of 3 members 2 of whom are clinicians with expertise in diabetology and one biostatistician. Members of the DMC are independent of those performing these studies, being neither Investigators nor employees of the Sponsor and without conflict of interest regarding study outcomes. For details, please refer to the DMC charter.

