11.5 INTERIM ANALYSIS

One interim analysis is planned for the purpose of efficacy to provide an early evaluation of Toujeo effectiveness, when approximately 1800 patients (54.2% information fraction of targeted sample size) have completed their 6-month (Day 180) visit.

Using a group sequential approach with a Gamma(-3) alpha-spending function and an overall two-sided alpha-level of 0.05, the two-sided nominal significance level is 0.010 at interim analysis, and 0.046 at final analysis.

If the targeted sample size (1800) cannot be reached, it could be considered to include a lower number of patients, however not below 1700. In this case, the nominal significance level to be spent at interim and at final 6-month analyses would be recalculated accordingly before the database lock for IA.

Overwhelming efficacy will be shown at interim analysis if the efficacy boundary is met, ie, if the two-sided p-value for comparison of primary composite endpoint incidence is below 0.010, with a difference in favor of Toujeo between percentages of patients reaching the primary composite endpoint. The corresponding power to show overwhelming efficacy at interim analysis under the alternative hypothesis is of 45%.

Scenario 1: If overwhelming efficacy is shown:

- The recruitment would be stopped (total sample size at that time estimated to be between 2600-3000 patients),
- The patients already enrolled would continue the study as planned,
- The results will be disclosed to the Sponsor and a communication plan to protect clinical data integrity is detailed in the DMC charter.

Scenario 2: If overwhelming efficacy is not shown:

- The study would continue as planned
- The Sponsor would not have access to any unblinded data,
- No results would be communicated.

For the interim analysis, analyses will be performed by an independent statistician external to the Sponsor. Results will be delivered directly to the independent Data Monitoring Committee for review.

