2.4.4.1 Analysis of primary efficacy endpoint

The primary efficacy analysis will be performed on the ITT population, using all post-baseline HbA1c data available and hypoglycemia events collected on the 6-month randomized period, regardless of IMP discontinuation.

The primary efficacy endpoint: proportion of patients reaching individualized HbA1c target at 6 months without documented symptomatic ($BG \leq 70$ mg/dL) hypoglycemia will be analyzed using a logistic regression model, adjusting for HbA1c target and other stratification factors used at randomization: SU use (y/n), GLP-1 RA use (y/n) and baseline HbA1c (as continuous). a superiority test will be performed to compare this proportion between treatment groups at IA

(2-sided, alpha = 0.010) and at final 6-month analysis (2-sided, alpha = 0.046). Treatment difference will be assessed by odds ratios and CIs. For the primary efficacy analysis, the randomization strata from IVRS will be used.

Patients with missing HbA1c data at 6 months will be regarded as not having reached HbA1c target. In order to examine the consistency of this analysis, the individual components of HbA1c target attainment and absence of any documented symptomatic (BG ≤70 mg/dL) or severe hypoglycemia will also be evaluated. Each individual component (HbA1c target attainment at 6 month, or absence of any documented symptomatic [BG ≤70 mg/dL] or severe hypoglycemia), will be compared between treatment groups, respectively, using same logistic regression model as the primary efficacy analysis.

Sensitivity analyses

The sensitivity analyses of primary efficacy endpoint will be performed at time of 6-month database lock.

- **On-treatment sensitivity analysis.**

A sensitivity analysis for the primary efficacy endpoint will be performed on the 6-month on-treatment period, as defined in [Section 2.1.3](#).

- **Multivariate analysis.**

As a sensitivity analysis, a multivariate analysis will be performed, adding the following baseline covariates in the model: BMI, duration of diabetes, baseline PAM score, hypoglycemic history and age. a backward selection procedure at 0.10 level will be used get the final model with these exploratory factors. Treatment effect will be re-evaluated based on the final model.

Country (USA/Canada) and US region effect systematic group difference will be explored.

- **Sensitivity analysis of primary efficacy endpoint with randomization strata from e-CRF.**

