3 INTERIM ANALYSIS

One IA of primary composite endpoint is planned for the purpose of overwhelming efficacy to provide an early evaluation of Toujeo effectiveness, when approximately 1800 patients (54.2% information fraction of targeted sample size) have completed their 6-month (Day 180) visit.

Using a group sequential approach with a Gamma (-3) alpha-spending function and an overall two-sided alpha-level of 0.05, the two-sided nominal significance level is 0.010 at IA, and 0.046 at final analysis.

If the targeted sample size (1800) cannot be reached, it could be considered to include a lower number of patients, however not below 1700. In this case, the nominal significance level to be spent at interim and at final 6-month analyses would be recalculated accordingly before the database lock for IA.

Overwhelming efficacy will be shown at IA if the efficacy boundary is met, ie, if the two-sided p-value for comparison of primary composite endpoint incidence is below 0.010, corresponding to an estimated difference of 5.8% in favor of Toujeo between percentages of patients reaching the primary composite endpoint.

The corresponding conditional power to show overwhelming efficacy at IA under the alternative hypothesis is of 45%.

For the IA, analyses will be performed by an independent statistician, external to the Sponsor. Results will be delivered directly to an independent Data Monitoring Committee (DMC) for review. a DMC meeting will be organized for this IA.

- Scenario 1: If overwhelming efficacy is shown:
 - The recruitment would be stopped (total sample size at that time estimated to be between 2600 and 3000 patients),
 - The patients already enrolled would continue the study as planned.
 - The results will be disclosed to the Sponsor and a communication plan to protect clinical data integrity is detailed in the DMC charter.
- Scenario 2: If overwhelming efficacy is not shown (probability of 55% under the alternative hypothesis):
 - The study would continue as planned, up to the final 6-month and 12-month analyses.
 - The Sponsor would not have access to any unblinded data.
 - No results would be communicated.

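### The interim effect is released only if it crosses a boundary of about 5.8 points, yet the plan corrects only the test levels: it sets no CI level, selection correction or caveat for the released estimate.

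*Protocol*

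**What the plan says.** - **The interim look.** The Protocol synopsis (Statistical considerations, Primary Analysis) provides for it: "One interim analysis is planned for the purpose of overwhelming efficacy on the primary composite endpoint when 1800 patients have been randomized" and have completed the 6-month visit.
- **Test levels.** Protocol 11.5 sets out the boundary: "Using a group sequential approach with a Gamma(-3) alpha-spending function and an overall two-sided alpha-level of 0.05", and "the two-sided nominal significance level is 0.010 at interim analysis, and 0.046 at final analysis".
- **Boundary as a difference.** SAP section 3 describes crossing at p<0.010 as "corresponding to an estimated difference of 5.8% in favor of Toujeo between percentages of patients" reaching the endpoint. The sample size sections (Protocol 11.1, SAP 1.3) assume 5.5 points.
- **Release rule.** Protocol 6.4.1 says that on a crossing the Sponsor sees the data and "results would be communicated in agreement with the DMC". Without a crossing the Sponsor sees nothing unblinded and nothing is communicated (Protocol 6.4.1 and 11.5, SAP section 3).
- **Use.** Protocol 6.3 gives the objective of the study and of the interim as "to generate real world evidence for the purpose of healthcare reimbursement and scientific communication only".
- **Estimate.** SAP 2.4.4.1 covers the interim and final tests with one logistic model, adjusted for HbA1c target, SU use, GLP-1 RA use and baseline HbA1c. It adds: "Treatment difference will be assessed by odds ratios and CIs". It gives no CI level and no estimate or interval that allows for the interim look.
- **Afterwards.** On a crossing, recruitment stops at roughly 2600 to 3000 patients (Protocol 6.4.1 says only that this could be considered). Enrolled patients continue, and the whole population is still analyzed at 6 and 12 months.

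**The concern.** An estimate that is published only when it is large is, on average, too large. Alpha spending protects the test from the extra look. It does nothing for the point estimate or its interval. Here the threshold for publication lies above the design effect, so if the planning assumption is exactly right, every released interim difference exceeds the truth.

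This matters more than usual because of what the interim is for. A reimbursement decision depends on how large the benefit is, not only on whether it exists. Under the plan's own 45% interim power, release is a likely outcome.

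**Working it through.** **Inputs.** Comparator rate 33% and difference 5.5 points, so 38.5% on Toujeo (Protocol 11.1); 1:1 allocation and 1800 patients at the interim, so 900 per arm; two-sided 0.010, so z = 2.576. Covariates are ignored, so figures from the adjusted model will differ slightly.

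**1. Reproducing the plan's figures.** The pooled rate is 35.75%. The pooled SE is √(2 × 0.3575 × 0.6425 / 900) = 2.259 points. The boundary is 2.576 × 2.259 = 5.82 points (SAP: 5.8). Power at the interim is 44.4% at level 0.010 (stated: 45%). Both reproduce.

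**2. Mean released difference.** For true difference δ, the SE is √{[p₁(1−p₁) + p₀(1−p₀)] / 900}, with p₀ = 0.33 and p₁ = 0.33 + δ. Put k = (5.8 − δ)/SE and P = 1 − Φ(k), the chance of release. The mean given release is δ + SE × φ(k)/P.

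At δ = 5.5: SE = √(0.457875/900) = 2.256 points; k = 0.3/2.256 = 0.133; P = 0.447; φ(k) = 0.395. The mean is 5.5 + 2.256 × 0.395/0.447 = 7.5 points, which is 36% too large. On the odds ratio scale the truth is (0.385/0.615)/(0.33/0.67) = 1.27, and the simulated geometric mean given release is 1.39.

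**3. Coverage given release.** In each scenario below, the boundary lies within 1.96 SE of the truth. An interval that misses low is therefore never released, and all the high misses are. Given release, a 95% CI misses with probability 0.025/P and a 99% CI with probability 0.005/P. At δ = 5.5 these are 0.025/0.447 = 5.6% and 0.005/0.447 = 1.1%.

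| True difference (points) | Released | Mean if released | 95% CI: lower limit above truth | 95% CI coverage | 99% CI coverage |
|---|---|---|---|---|---|
| 3.0 | 10.6% | 6.9 | 23.7% | 76.3% | 95.3% |
| 4.0 | 21.1% | 7.1 | 11.8% | 88.2% | 97.6% |
| 5.5 | 44.7% | 7.5 | 5.6% | 94.4% | 98.9% |
| 7.0 | 70.2% | 8.1 | 3.6% | 96.4% | 99.3% |

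Simulated binomial interims using the actual test agree: 44.4% released at 5.5 points, means within 0.1 point of the table, and 95% CI coverage of about 77%, 88%, 94.3% and 96.3%. Coverage is exactly 95% when the truth equals the boundary.

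**4. Whole-population estimate after a crossing.** The 1800 interim patients carry their selected mean and later patients average the truth. At δ = 5.5 this gives (1800 × 7.5 + 800 × 5.5)/2600 = 6.9 points, or (1800 × 7.5 + 1200 × 5.5)/3000 = 6.7.

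**5. A standard bias-adjusted estimate.** Whitehead's estimate corrects bias averaged over crossing and not crossing, which is only about 0.4 points at δ = 5.5. It moves an observed 7.5 to about 7.15, removing about 0.35 of the 2.0-point excess.

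**The case against.** The case against has several good parts.

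- **Error control is in place.** The levels 0.010 and 0.046 give an overall two-sided alpha of about 0.0503 on recalculation. Upward bias after an early crossing is common to efficacy stopping rules and is not peculiar to this trial. That stands: the point concerns estimation and reporting, not the validity of the test.
- **Coverage.** A reader might infer that an ordinary 95% CI generally undercovers after release. It does not. The loss is under 1 point at the design effect, coverage is above nominal beyond 5.8 points, and it is materially low only for true effects well below design, where release is also less frequent (21% at 4 points, 11% at 3). What remains at 5.5 points is one-sided: the lower limit is too high in 5.6% of releases against a nominal 2.5%.
- **The 95% level is my assumption.** SAP 2.4.4.1 states none for the primary odds ratio, although the SAP's hypoglycemia sections do say 95%. The supportable defect is the missing level.
- **What is released, and to whom.** A reader might infer that a raw interim odds ratio goes to payers. The odds ratio is covariate-adjusted, and no passage names the statistic or the recipient. The communication plan is in the DMC charter, which is not available here and may carry caveats. Protocol 6.3 supports only the purpose, and the SAP cites the charter for protecting data integrity, not for estimation.
- **The later analysis.** The interim is not the last word, since the whole-population analysis follows either way. But the interim patients make up most of it, so the excess shrinks without disappearing, and nothing in the Protocol or SAP says that it supersedes the released figure.

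**Conclusion.** The point holds as one about estimation. With 900 per arm, a 33% comparator rate and release at p<0.010, a released interim difference averages 7.5 points if the truth is 5.5, 7.1 if it is 4, and 6.8 to 6.9 if it is 3. The released figure therefore hardly distinguishes a small benefit from the planned one. After a crossing at a true 5.5, the whole-population estimate still averages 6.7 to 6.9.

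Interval coverage is a secondary matter, serious only if the true effect is well below design and only if a 95% CI is used. Neither the type I error plan nor the boundary is in question. Because the result is meant for reimbursement use and the remedy is small, the text should be settled before the interim database lock.

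**What to change.** In SAP section 3 and SAP 2.4.4.1:

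1. Report the interim odds ratio and difference with a 99% CI, and the final 6-month ones with a 95.4% CI, so that the intervals match the 0.010 and 0.046 tests. Recalculate the CI levels if the nominal levels are recalculated, as the plan allows when fewer than 1800 patients are included.
2. State that a released interim effect size is preliminary, is likely overstated because it is released only on crossing, and is superseded by the whole-population 6-month analysis. Check that the communication plan in the DMC charter says the same.
3. Optionally, show beside it an estimate conditional on crossing, which targets the release rule directly. A Whitehead estimate alone would leave most of the excess in place.

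The cost is a few lines of SAP text and standard programming, a wider interval and a less favorable quoted effect. Sample size, boundary and conduct do not change. The wider interval does not remove the bias in the point estimate, which is why item 2 is needed as well as item 1.
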